14.5 Missing data

Few missing data were observed in past trials in this pathology. Due to likely expected loss of efficacy after treatment discontinuation, and a possible deterioration compared with baseline values, last or baseline observation carried forward may not be appropriate. Missing values will be imputed using a linear model estimated on the Placebo group. The potential impact of missing data on the study's conclusions will be evaluated. Descriptive data analyses will allow assessing the pattern of missing data, including reasons for drop-outs in each treatment group. In addition, sensitivity analyses will be conducted by using other missing data approaches (further details in the SAP).

For any patient experiencing early trial interruption, an early interruption visit is planned. It will be checked if this visit took place within a given time frame where the next regular visit would have been planned. In case the early interruption visit occurs within this time frame, data of the early interruption visit will be shifted to the next regular visit for all analyses. In case the early interruption visit does not occur within this time frame, the data of the early interruption visit will not be included in any of the inferential analyses.

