V1.4	05DEC2017	Rationale for moving from V1.4 to V1.5: due to an unexpected investigational medicinal product (IMP) quality event, without safety concerns, the use of dose 2 IMP is discontinued from the pivotal phase III study CLN-PXT3003-02 upon Sponsor decision (September 18 th , 2017). The stability testing at Quay Pharma (UK) observed the occurrence of crystals in one stability batch of PXT3003 dose 2 at month 18 (September 14 th , 2017), whereas this was not the case at month 12. This new finding is inconsistent with the dose 2 IMP release criteria and therefore does not meet the ICH Harmonized Tripartite Guideline for Stability Testing of New Drug Substances and Products. Hence, the patient arm of PXT3003 dose 2 will early terminate the study. They will be offered to enter the extension study CLN-PXT3003-03 to receive the equivalent of dose 2 (5 mL per administration), by using of its equivalent dose, i.e. twice the dose 1 IMP (2x5 mL, i.e. 10 mL) per administration. Furthermore, all patients using dose 1 IMP or placebo will continue to receive dose 1 IMP or placebo (5 mL per administration) in the pivotal phase III study CLN-PXT3003-02 as planned.

IMPACTED OF THE PROTOCOL AMENDMENT V1.4

1. How to manage the dose 2 patient group discontinuation?	
The PXT3003 dose 2 study arm will discontinue prematurely from study CLN-PXT3003-02, in accordance with section 11.6.1 "if the study is prematurely discontinued then enrolled patients should be called for an end of study visit".
 
Hence, there is no need to implement additional information in the protocol.
 
The sites will receive additional useful instructions to organise the recall of dose 2 IMP patients.

2 Statistical sections: how to manage incomplete data	
Due to incomplete data in the dose 2 arm, the missing data will be evaluated as described in the section 14.5 of the protocol.

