14. STATISTICAL CONSIDERATIONS

14.1 Analysis sets

The **Full Analysis Set (FAS)** will be constituted by all the randomized patients.

The **Per-Protocol (PP)** population will include all the patients of the FAS without major protocol violation during the course of the study.

All the efficacy analyses will be conducted on the FAS population and reproduced on the PP population for sensitivity purposes. The safety analyses will be conducted on the FAS, given that all randomized patients will receive at least one dose of treatment.

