14.2 Primary efficacy analysis

The significance of the studied drug effect compared with Placebo will be tested by an Analysis of Covariance (ANCOVA) on the summary mean of ONLS at 12 and 15 months adjusted for baseline ONLS values. ANCOVA will be featured by a Linear Mixed Model (LMM), including baseline ONLS values and treatment as fixed factors, and center as random effect. The use of two repeated post-baseline measures increases the power to detect treatment differences in mean levels of the outcome measure over time (Frison and Pocock, 1992; Morgan and Case, 2013).

Two active doses will be compared to Placebo. As the monotonicity of dose effect is not assumed, each dose will be compared at a two-sided 2.5% significance level, in order to preserve an overall false-positive rate of 5%.

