14.3 Sample size calculation

Assuming ANCOVA with 2 post-baseline measures, a linear correlation coefficient of ONLS of $R = 0.75$ between baseline and end of the study, a standard deviation of ONLS of $SD \approx 1$, and a negligible between center standard deviation (estimated $SD = 0.13$ [0;0.35]), the resulting adjusted standard deviation $ASD \approx [1*(1-.75^2)]^{.5} \approx 0.65$, thus a minimum clinically relevant difference in ONLS should be a Cohen's Δ of $0.65/2 \approx 0.325$, rounded to $\Delta = 0.3$. From calculations based on compound symmetry of the covariance matrix (Frison and Pocock, 1992, Morgan and Case, 2013), such a difference should be detected versus Placebo with a power of 90% at a two-sided 2.5% significance level when the sample size reaches at least 89 patients per group. Assuming a drop-out rate of $\approx 10\%$, we anticipate recruiting 100 patients per group for a total of at least 300 patients.

The parameters needed for sample size calculation were evaluated based on historical trials (Micallef, Attarian *et al.*, 2009; Pareyson, Reilly *et al.*, 2011; Attarian, Vallat *et al.*, 2014).

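### Read literally, predicting lost dose 2 scores from a placebo line would shrink the pooled variance and put the dose 1 test at about 2.7% to 4% instead of 2.5%

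*Combined protocol and SAP*

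**What the plan says.** - **Imputation rule.** Section 14.5: "Missing values will be imputed using a linear model estimated on the Placebo group". It does not name the predictors, say whether imputation is single or multiple, or mention added noise.
- **Use for dose 2.** Item 2 of the impact list for amendment V1.4: "Due to incomplete data in the dose 2 arm, the missing data will be evaluated as described in the section 14.5 of the protocol".
- **Analysis set.** Under 14.1 the full analysis set "will be constituted by all the randomized patients", so dose 2 patients stay in the efficacy analysis.
- **Primary model.** Section 14.2, for the average of the month 12 and month 15 ONLS: "ANCOVA will be featured by a Linear Mixed Model (LMM), including baseline ONLS values and treatment as fixed factors, and center as random effect". No variance by arm is described. One fit to all three arms is implied but not stated.
- **Error rate.** Section 14.2: "each dose will be compared at a two-sided 2.5% significance level, in order to preserve an overall false-positive rate of 5" percent.
- **Deferred detail.** Section 14.5 adds that "sensitivity analyses will be conducted by using other missing data approaches (further details in the SAP"). The document contains no separate SAP text.

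**The concern.** A score predicted from the placebo regression lies on that line and leaves almost no residual. With a few such scores spread evenly over the arms, little happens. After the dose 2 stop they are concentrated in one arm. A residual variance pooled over three arms would then be pulled down by dose 2 patients whose scores were never observed, and the same variance sets the standard error for dose 1 versus placebo.

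Dose 1 is the comparison whose treatment arm continues as planned under V1.4. On this reading its 97.5% interval would be too narrow and its false-positive rate above the level assigned to it. This concerns error bars. It is separate from the bias that placebo-based imputation puts into the dose 2 estimate.

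**Working it through.** **1. The plan's own sample size.** Section 14.3 assumes "a linear correlation coefficient of ONLS of $R = 0.75$ between baseline and end of the study", SD about 1, a difference of 0.3, 90% power, two-sided 2.5% and compound symmetry. The residual variance of the two-visit mean given baseline is

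V = SD² × [(1 + R)/2 − R²] = 0.875 − 0.5625 = 0.3125.

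n = 2 × (2.2414 + 1.2816)² × 0.3125 / 0.3² = 86.2, so 87 per group (88 with the t distribution). The plan states 89, so V = 0.3125 fits its assumptions.

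**2. Residual variance left by a predicted patient (no noise added).**
- Both visits predicted from baseline: about 0.
- Month 15 only, predicted from baseline: (1 − R²)/4 = 0.4375/4 = 0.109, a ratio to V of 0.35.
- Month 15 only, predicted from baseline and month 12: the month 12 coefficient is R/(1 + R) = 0.429, so the variance is (1.429/2)² × 0.4375 = 0.223, a ratio of 0.71.

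**3. Missing shares in dose 2 (assumption).** The documents give no counts. The stop was on 18 September 2017. Month 15 (day 450) is reached by then if randomisation was by 25 June 2016, and month 12 (day 360) if by 23 September 2016. The synopsis plans one year of recruitment, Q4 2015 to Q4 2016. With even accrual and no recall visit moved to a scheduled visit:
- Start 1 October 2015: 268/365 = 73% have both visits, 90/365 = 25% lack month 15 only, 7/365 = 2% lack both.
- Start 31 December 2015: 177/366 = 48%, 90/366 = 25%, 99/366 = 27%.
- A start in early December 2015 gives roughly 55%, 25% and 20%.

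**4. Level of the dose 1 test.** With equal arms, c the complete share of dose 2, m the share lacking month 15 only and r the ratio from step 2:

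q = (2 + c + r × m)/3, and true level = 2 × [1 − Φ(2.2414 × √q)].

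| Both / month 15 lost / both lost | Predictors | q | 2.2414√q | Level |
|---|---|---|---|---|
| 73 / 25 / 2 | baseline | 0.939 | 2.172 | 3.0% |
| 73 / 25 / 2 | baseline, month 12 | 0.970 | 2.207 | 2.7% |
| 55 / 25 / 20 | baseline | 0.879 | 2.102 | 3.6% |
| 55 / 25 / 20 | baseline, month 12 | 0.910 | 2.138 | 3.3% |
| 48 / 25 / 27 | baseline | 0.856 | 2.074 | 3.8% |
| 48 / 25 / 27 | baseline, month 12 | 0.886 | 2.110 | 3.5% |
| 0 / 0 / 100 (limit) | baseline | 0.667 | 1.830 | 6.7% |

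The standard error is too small by the factor √q. For the even-accrual rows √q runs from 0.985 to 0.925, so the interval is 1.5% to 7.5% too narrow. If 45% lacked both visits (30% complete, 25% lacking month 15 only), q = (2 + 0.30 + 0.0875)/3 = 0.796 and the shortfall is about 11%.

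**5. Simulation.** With 100 per arm and no treatment effect, 8,000 trials per setting over the 2% to 27% range give 2.7% to 4.1% for dose 1. A model on dose 1 and placebo only gives 2.3% to 2.8%. In the 20% case, imputing 10% of dose 1 and placebo as well gives 3.1%. A random centre effect (SD 0.13 from 14.3, 20 centres assumed, 6,000 trials) gives 3.7%, simulation SE 0.24 points.

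**6. Dose 2 and the overall rate.** Predicted dose 2 scores reproduce the placebo line, so the dose 2 difference varies less than its standard error implies. Its test has size about 0.2% to 2%. The chance of any false positive with no effect in either dose is about 3.7% to 4.7%.

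**The case against.** The strongest reply is that the inflation needs two conditions the text leaves open. The sentence in 14.5 also fits a stochastic or multiple placebo-based imputation, and 14.2 never says that both contrasts come from one fit. If either condition fails, the level is about 2.5%. This stands: a reader might infer that the test certainly exceeds its level, and the documents do not support that. They also do not rule it out, and the literal reading is the one that goes wrong.

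A reader might also infer a breach of the overall 5%. Step 6 shows none at plausible shares; it would take nearly all of dose 2 being imputed.

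Larger figures are possible only under accrual later than even, for which the documents give no basis. Section 14.5 also moves in-window early-interruption scores to the next scheduled visit, which reduces the loss. Any fall in dose 2 power should not be put down to the variance alone: in the 55/25/20 case with baseline-only prediction, a true difference of 0.3 shrinks to 0.3 × (0.55 + 0.25/2) = 0.20 in the estimate itself.

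Nor can dose 1 and placebo be called untouched, since the synopsis reports a longer study interruption in Germany. Finally, the promised sensitivity analyses might expose a wrong standard error, but they do not change the primary test.

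**Conclusion.** The point holds in conditional form. If the predictions carry no noise and the residual variance is pooled over three arms, dose 1 versus placebo would be tested at about 2.7% to 4% instead of 2.5%. The interval would be a few percent too narrow, up to about 10% if more of dose 2 is imputed. The figures rest on the inputs in 14.3, 100 per arm, compound symmetry, even accrual over the planned dates and no recall scores moved. With small dose 2 loss and month 12 as a predictor the level is close to nominal.

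The error lies in the per-dose level and the dose 1 interval, not in the overall 5%. It is a should-fix: modest in size, but it bears on a primary comparison. Left open, the choice of imputation and model could also be made after the data are seen, and it moves the primary p-value.

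**What to change.** - **14.2 and SAP:** state that dose 1 versus placebo is tested in a model fitted to those two arms only, or in a model with a separate residual variance per arm. The two-arm model is the simpler choice and keeps imputed dose 2 scores out of this test altogether.
- **14.5:** replace bare predictions with placebo-based multiple imputation that draws both parameters and residuals, with months 12 and 15 drawn jointly, and name the predictors.

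In simulation either change returns the dose 1 level to about 2.5%: 2.6% for the two-arm model, and 2.4% to 2.5% for proper draws, even with all of dose 2 imputed. The cost is SAP wording and a little code. With 100 per arm, error degrees of freedom fall from 300 − 4 = 296 to 200 − 3 = 197, which barely moves the critical value. No new data are needed.

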14.6 Safety analyses

Safety and tolerability will be assessed by summarizing and analyzing adverse events (AEs), change in physical examination, vital signs, electrocardiogram (ECG) and laboratory data.

The incidence of Treatment Emergent Adverse Events (TEAEs), related AEs (including possibly and probably related AEs) with moderate or severe intensity, AEs leading to withdrawal of study drug, and Serious Adverse Events (SAEs) will be summarized by treatment groups. This summary will show

incidence rates (number and percentage of patients) with corresponding 95% confidence intervals. Moreover, 95% confidence intervals for the difference in incidence rates between each group will be calculated.

Changes in physical examination, vital signs (blood pressure and heart rate) and ECG will be analyzed descriptively.

Changes from baseline to the end of the treatment period in laboratory values for hematology and blood chemistry will be summarized descriptively. Each laboratory value will be flagged to show whether it lies within, below, or above the normal range. The proportion of subjects with values in each of these categories at each assessment will be also summarized.

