3 Section 11.7 follow up extension study – adapted as followed	
Patients who completed this 15-month study or who were prematurely discontinued from the PXT3003 dose 2 administration will be offered to enter the open-label extension study CLN-PXT3003-03.
 
Patients previously assigned to dose 2 PXT3003 will receive the equivalent of dose 2 (i.e. 5 mL per administration), by use of its equivalent dose, i.e. twice the dose 1 PXT3003 (2x5 mL, i.e. 10 mL per administration) in the study CLN-PXT3003-03.
 
Patients previously assigned to dose 1 PXT3003 or placebo and who have completed the pivotal phase III study will receive dose 1 PXT3003 (5 mL) in the study CLN-PXT3003-03.
 
Hence the protocol of extension study has been amended to assign all placebo patients to dose 1 IMP only, whereas patients previously assigned to dose 1 IMP will continue to do so. As a consequence of the difference of IMP volume (i.e. 5 mL and 10 mL) to be administered the study has become an open-label study that no longer randomizes patients to study treatment.

Signature page for sponsor representative**PROTOCOL CLN-PXT3003-02****STUDY PLEO-CMT (PLEO-CHARCOTMARIETOOTH)**

**International, multi-center, randomized, double-blind, placebo-controlled phase III study assessing
in parallel groups the efficacy and safety of 2 doses of PXT3003
in patients with Charcot-Marie-Tooth Disease type 1A treated 15 months**

EUDRACT N° 2015-002378-19**IND N° 122505****Protocol version: N° 1.4 dated December 05th 2017**

The study will be conducted in compliance with the following protocol and will be carried out in accordance with Good Clinical Practice (GCP) as required by the ICH GCP E6 and local applicable regulatory requirements in the participating countries.

Rationale for moving from V1.3 to V1.4: due to an unexpected investigational medicinal product (IMP) quality event, without safety concerns, the use of dose 2 IMP is discontinued from the pivotal phase III study CLN-PXT3003-02 upon Sponsor decision (September 18th, 2017).

The stability testing at Quay Pharma (UK) observed the occurrence of crystals in one stability batch of PXT3003 dose 2 at month 18 (September 14th, 2017), whereas this was not the case at month 12. This new finding is inconsistent with the dose 2 IMP release criteria and therefore does not meet the ICH Harmonized Tripartite Guideline for Stability Testing of New Drug Substances and Products.

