Hence, the use of PXT3003 dose 2 will be prematurely discontinued from the study. Patients assigned to PXT3003 dose 2 will therefore be withdrawn from study CLN-PXT3003-02 upon completion of the end-of-study assessments and will be offered to enter the extension study CLN-PXT3003-03 to receive the equivalent of dose 2 IMP (5 mL per administration), by use twice the dose 1 IMP (2x5 mL, i.e. 10 mL) per administration.

Furthermore, all patients using dose 1 IMP or placebo will continue to receive dose 1 IMP or placebo (5 mL per administration) in the pivotal phase III study CLN-PXT3003-02 as planned.

I fully agree to the contents of this protocol which gives all the necessary information to conduct this study. I hereby accept to coordinate this study:

The site investigator Date :

Name:

Hospital: Signature:

Address:

Summary of Changes

From V1.3 to V1.4

Nº Changes Page / section	V1.3 (Initial text)	V1.4 (Text modified)
Each page (heading)	Protocol CLN-PXT3003-02, Version 1.3	Protocol CLN-PXT3003-02, Version 1.4
Pages: 1-4-5-6	
Protocol version: N° 1.3 and rationale moving from V1.3 to V1.4
	
Protocol version N°1.4
 
Rationale for moving from V1.3 to V1.4: due to an unexpected investigational medicinal product (IMP) quality event, without safety concerns, the use of dose 2 IMP is discontinued from the pivotal phase III study CLN-PXT3003-02 upon Sponsor decision (September 18th, 2017).
 
The stability testing at Quay Pharma (UK) observed the occurrence of crystals in one stability batch of PXT3003 dose 2 at month 18 (September 14th, 2017), whereas this was not the case at month 12. This new finding is inconsistent with the dose 2 IMP release criteria and therefore does not meet the ICH Harmonized Tripartite Guideline for Stability Testing of New Drug Substances and Products.
 
Hence, the patient arm of PXT3003 dose 2 will early terminate the study. They will be offered to enter the extension study CLN-PXT3003-03 to receive the equivalent of dose 2 (5 mL per administration), by using of its equivalent dose, i.e. twice the dose 1 IMP (2x5 mL, i.e. 10 mL) per administration.
 
Furthermore, all patients using dose 1 IMP or placebo will continue to receive dose 1 IMP or placebo (5 mL per administration) in the pivotal phase III study CLN-PXT3003-02 as planned.

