Extension study, a DB 9-month Follow-up	
In order to stimulate the recruitment and motivate patients to be enrolled, patients having completed the 15-month study will be eligible to receive PXT3003 in a follow-up extension trial for 9 months if they are willing to continue the treatment. They will be attributed to active drug by a second randomization. This 9-month extension study will provide additional long-term data on safety and additional efficacy data that could provide some evidence of disease modifying effect.

Planned dates	
 - CTA & IND submission: from June 2015 - Start (First patient in): Q4 2015 - Patients recruitment: 1 year (end of recruitment: Q4 2016) - Study duration for each patient: 15-month double-blind period - Last patient out (ie., end of study): expected Q1 2018 in all the countries, except in Germany where the LPO is expected Q3 2018* - Clinical Study Report: expected Q2 2019 
* due to longer interruption of the study in Germany regarding the occurrence of crystals in the dose 2 IMP, the LPO in Germany is expected in Q3 2018

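### Section 14.6 compares adverse events as crude percentages although only dose 2 was stopped early, which modestly understates dose 2 incidence for events that can occur late

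*Combined protocol and SAP*

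**What the plan says.** Section 14.6 covers four AE categories: treatment-emergent events, related events of moderate or severe intensity, events leading to withdrawal of study drug, and serious events. Each is reported by group as "incidence rates (number and percentage of patients) with corresponding 95% confidence intervals". It adds that "95% confidence intervals for the difference in incidence rates between each group will be calculated". The measure is called a rate, but its denominator is patients, not time. On the population, 14.1 says "The safety analyses will be conducted on the FAS", which is everyone randomised.

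The V1.4 rationale in the front matter says "the use of PXT3003 dose 2 will be prematurely discontinued from the study". The reason given is "due to an unexpected investigational medicinal product (IMP) quality event, without safety concerns". The decision is dated 18 September 2017. Dose 2 patients leave after end-of-study assessments and are offered the extension study, while dose 1 and placebo carry on as planned. The amendment's only statistical instruction for the incomplete dose 2 data is to follow 14.5. That section deals with imputing missing values and placing early-interruption visits; it says nothing about time at risk for AEs. Section 14.6 contains no person-time denominator, time-to-event method or common cut-off.

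**The concern.** A crude percentage counts a patient observed for 9 months and one observed for 15 months alike. When one arm is observed for less time, its expected percentage is lower even if the true risk is the same. Here the shortfall falls on dose 2 alone, the dose that the Rationale (section 7) describes as not previously tested. Comparison of safety with placebo is a stated endpoint (8.4.2). For events that can still occur late in treatment, the planned difference and its interval are therefore shifted in dose 2's favour.

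**Working it through.** **Plan's own figure.** The documents give no expected AE incidence or precision for this comparison, so there is none to reproduce.

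**Inputs from the documents.** Planned follow-up is 450 days (11.1). First patient in is planned for Q4 2015, with one year of recruitment ending in Q4 2016 (Synopsis, Planned dates). The stop is taken as 18 September 2017 (V1.4 rationale). There are 100 patients per group (Synopsis). Phase II placebo TEAE incidence was 47% over 12 months (6.4), used only as one illustrative level.

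**Assumptions.** Recruitment is uniform over the dates shown, the true hazard is identical in dose 2 and placebo, there is no other drop-out, and dose 2 time at risk ends on the decision date.

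**Step 1: exposure.** Exposure is e = min(450, stop date − randomisation date). Counting back 450 days from 18 September 2017 gives 25 June 2016, so anyone randomised later is cut short. For the latest case, 25 June to 31 December 2016 is 189 days of a 366-day recruitment period: 189/366 = 51.6%. The mean loss is 0.516 × 189/2 = 48.8 days, leaving 401.2 of 450 (89.2%). For the earliest case, 97/365 = 26.6%. The loss is 0.266 × 97/2 = 12.9 days, leaving 437.1 (97.1%).

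**Step 2: crude incidence under constant hazard.** With h = −ln(1−p)/450, s the share cut short and m the shortest exposure:

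incidence = (1−s)·p + s·[1 − (e^(−hm) − e^(−450h)) / (h(450−m))]

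Latest case, p = 47%: h = 0.6349/450 = 0.001411; e^(−261h) = 0.692; the bracket is 1 − (0.692 − 0.530)/0.2666 = 0.393; the total is 0.484 × 0.47 + 0.516 × 0.393 = 43.0%.

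| Recruitment assumed | Cut short | Mean exposure | Shortest | 20% reads | 30% reads | 47% reads | 60% reads |
|---|---|---|---|---|---|---|---|
| 1 Oct 2015 – 30 Sep 2016 | 26.6% | 97.1% | 353 d | 19.5% | 29.3% | 46.0% | 58.9% |
| 15 Nov 2015 – 15 Nov 2016 | 39.1% | 93.8% | 307 d | 18.9% | 28.4% | 44.8% | 57.5% |
| 1 Oct 2015 – 31 Dec 2016 | 41.4% | 91.3% | 261 d | 18.4% | 27.7% | 43.8% | 56.4% |
| 31 Dec 2015 – 31 Dec 2016 | 51.6% | 89.2% | 261 d | 18.0% | 27.2% | 43.0% | 55.5% |

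At 30-60% incidence the bias is −0.7 to −4.5 points.

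**Step 3: early events.** Let H = −ln(1−p), with 70% of H spread over the first 90 days and 30% over the remaining 360. The same recruitment cases, in order, give biases of −0.19, −0.42, −0.59 and −0.73 points at 20%, and −0.40, −0.89, −1.25 and −1.56 at 60%. For events confined to the two titration weeks the bias is essentially nil, since the shortest exposure is 261 days.

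**Step 4: would patient-year rates repair it?** Under the Step 3 pattern at 20%, with equal true risk, the crude ratio (dose 2/placebo) is 0.990, 0.979, 0.971 and 0.963. The ratio of events per time at risk is 1.018, 1.041, 1.058 and 1.075. In the latest case, mean time to first event or censoring is 381.2 days on placebo and 341.5 on dose 2, so 0.963 × 381.2/341.5 = 1.075. With front-loaded events the patient-year comparison is further from 1 than the crude one, and against dose 2.

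**Step 5: scale against precision.** The 95% half-width for a difference with 100 per arm is 1.96 × √(2p(1−p)/100): 11.1 points at 20%, 13.8 at 47%. A simulation with 100 per arm, constant equal hazards and 15 calendar months in place of 450 days put the interval wholly below zero in about 3-6% of trials at 20% incidence and 4-11% at 55%, against a nominal 2.5%.

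**The case against.** The strongest reply is that the effect is small: at most about 5 points against half-widths of 11-14. Section 14.6 has no safety test, margin or decision rule for it to distort. This stands, and it limits the weight of the point. It does not remove it, because the shift is systematic and avoidable.

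A reader might infer that every AE comparison is tilted toward reassurance. The documents do not support that. Treatment starts at half dose to improve tolerability (10.1), so an early concentration of events is plausible, and for such events the bias is slight or nil.

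A reader might also infer that patient-year rates are the natural main analysis. Step 4 shows why not: they rest on a roughly constant hazard, which nothing in the documents establishes.

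The dates are uncertain. 18 September 2017 is a decision date, not a documented last dose, and dose 2 patients remain until their end-of-study assessments, so the shortfall may be somewhat overstated. Recruitment dates are planned; later enrolment would enlarge it. Last patient out in Q1 2018 outside Germany, less 450 days, implies a last randomisation between 8 October 2016 and 5 January 2017 if nothing was delayed, which leans toward the larger values. The longer interruption in Germany makes on-drug time there unclear.

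Finally, section 14.9 defers further detail to a SAP that is not in the file. An equal-follow-up analysis may be specified there. What can be said is that 14.6 as given does not contain one and V1.4 did not add one.

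**Conclusion.** The point holds as a modest one that should be fixed. Followed as written, 14.6 understates dose 2 incidence relative to placebo for any event with risk after the stop. The size is about 1-5 points at 30-60% incidence under constant hazard, about 0.2-1.6 points at 20-60% with 70% of the hazard in the first 3 months, and near zero for titration-period events. These figures rest on uniform recruitment within the planned dates, equal true hazards, and time at risk ending on the decision date; actual enrolment and last-dose dates are not given. The documents do not support the stronger conclusions that the bias affects all AEs or that the dose 2 safety comparison is invalid as a whole.

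**What to change.** In 14.6, base the dose 2 versus placebo AE comparison on equal follow-up, by one of two routes, with 95% intervals for the difference:

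- **Common calendar cut-off.** Count events in all three arms only up to one stated date, the dose 2 stop. Randomisation then gives the arms the same follow-up distribution, with no assumption about the hazard.
- **Kaplan-Meier cumulative incidence at a common time**, with dose 2 patients censored administratively. Because the stop was for product quality and not safety, censoring by the stop can reasonably be treated as unrelated to AE risk. Under the dates above, 48-73% of dose 2 patients could reach 450 days, so the 15-month estimate is obtainable.

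Report patient-year rates as supportive only, and keep the full crude table as descriptive. State the cut-off date and the AE window used: 8.4.2 records events to the end of the study, while 12.1.1.1 ends reporting one month after the last dose, and the two need reconciling.

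The cost is a paragraph and a few tables. Event onset dates (12.1.2) and drug administration dates (17.2) are already collected. The downside is that events in the continuing arms after the cut-off do not enter the cut-off comparison; the descriptive table still shows them.
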